#### 4.1 Baseline Clinical Data

Data collected will include demographics, the pre-admission symptoms, pre-admission therapy, preadmission exercise tolerance and performance status (retrospective assessment by the patient and/or representative 6 weeks preceding admission) level of educational attainment, past-medical history, time and route of admission, and in-hospital routine physiological observations (including heart rate, blood pressure, oxygen saturation, respiratory rate and temperature). Blood biomarkers that are part of clinical profiling such as CRP, total blood count, D-Dimers and IL-6 as well as exploratory markers for Long covid mechanisms including inflammatory responses and clotting factors. This will also be performed pre and post (30mins) exercise bouts..

##### 4.1.1 Anthropometrics (Session 1)

Participants will be asked to provide an approximate date of onset of COVID-19 and whether they have received any COVID-19 vaccinations and the manufacturer of the vaccine. Body Mass (kg) and height (m) will be assessed.

##### 4.1.2 Questionnaires

###### 4.1.2.1 Symptom Profile

Symptom profile will be measured twice at the baseline assessment (Day 0), to capture a) retrospective assessment by the patient of their symptom status at symptom onset (essentially their baseline symptoms), and b) their current symptom status at the point of testing.

###### 4.1.2.2 Quality of Life

The EQ-5D-5L is routinely used in the assessment of the quality of life in respiratory research and is available in more than 130 languages (EQ-5D-5L). It comprises five dimensions (Previously 3): mobility, self-care, usual activities, pain/discomfort, and anxiety/depression. Each dimension has five levels: no problems, slight problems, moderate problems, severe problems, and extreme problems.

###### 4.1.2.3 Sleep Behaviour

Participants will complete the Pittsburgh Sleep Quality Index (PSQI). The PSQI is a self-report measure to assess sleep quality over a 4 week in period, throughout the

intervention. The measure consists of 19 individual items, with a 0-3 interval scale and creates 7 components that produce one global score. The PSQI is reliable and valid in the assessment of sleep problems.

#### **4.1.2.4 Fatigue**

Fatigue is a common complaint in patients recovering from an acute respiratory infection and is not adequately captured in general quality of life or specific recovery questionnaires. Participants will complete 2 separate measures of fatigue at Visit 1 and Visit 2); (A) the Fatigue Assessment Scale (FAS), a self-reported questionnaire validated to assess presence and severity of fatigue; and (B) MFI-20. A 20 item self-reported questionnaire assessing fatigue across five aspects.

#### **4.1.2.5 MRC Dyspnoea Scale**

The Medical Research Council (MRC) Dyspnoea Scale (MRC) is a measure to grade the effect of breathlessness on the person's daily activities. The MRC is simple to administer and is a short 1-5 stage scale (1 item) and allows the person to state the extent to which their breathlessness affects their mobility.

#### **4.1.2.6 Post-COVID-19 Functional Status (PCFS) Scale**

The Post-COVID-19 Functional Status (PCFS) Scale will be assessed upon discharge from the hospital and during each face-to-face visit to monitor direct recovery and to assess functional sequelae. The PCFS will evaluate the ultimate consequences of COVID-19 on functional status and supplement other instruments that measure quality of life, tiredness, or dyspnoea in the acute phase. The PCFS covers the full spectrum of functional outcomes and focuses on both limitations in usual duties/activities and changes in lifestyle in six scale grades. Briefly grade 0 reflects the absence of any functional limitation, and the death of a patient is recorded in grade D. Upward of grade 1, symptoms, pain or anxiety are present to an increasing degree. This has no effect on activities for patients in grade 1, whereas a lower intensity of the activities is required for those in grade 2. Grade 3 accounts for inability to perform certain activities forcing patients to structurally modify these. Finally, grade 4 is reserved for those patients with severe functional limitations requiring assistance with activities of daily living (ADL).

#### **4.1.2.7 Cognition**

The Montreal Cognitive Assessment (MoCA) will be conducted at Visit 1. To allow accurate interpretation, highest educational level/attainment will be recorded during data collection

### **4.1.3 Functional Status**

Two different assessments of lower extremity functional capacity will be conducted at each visit these are (A) the 6-minute walk test (6MWT) and (B) the timed up and go test (TUG). The 6MWT is a standardised and widely used measure of functional status in individuals with chronic disease such as chronic obstructive pulmonary disease, cystic fibrosis, congestive cardiac failure, peripheral vascular disease, and elderly. It has been previously used to assess response to interventions and predict morbidity and mortality. Participants will be given a shortened practice attempt (1-2 minutes) at the beginning of each of their assessment visits. This will not be recorded but will be performed to allow familiarisation with the assessment and repeated at each visit for

consistency. Patients suffering from excessive fatigue/Post exertional malaise from the 6MWT will be excluded from the study to prevent further onset of these symptoms.

The TUG is reliable and reproducible and has been validated as a predictor of frailty and risk of falls in elderly adults. The TUG has several advantages over other measures, mainly its reproducibility and shorter assessment time. Its use at predicting functional status following pneumonia has not been assessed previously.

Participants will also be asked to self-report their return to functional activity and employment at each contact with the research team (telephone consultations and follow-up visits.) Each participant will be asked at each contact with the research team if they have returned to perform their activities of daily living to the same level as 6 weeks before admission, and if they have returned to their occupation (if employed.) The patient-reported date of return to these activities will also be recorded.

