### 2.2 Secondary Aims

- Examine the relationship between COVID-19 symptom prevalence and exercise tolerance
- Examine the prevalence of post-exertional malaise in people with long covid.
- Examine the role of vaccination history (COVID-19) on exercise tolerance.

- Assess cardio-respiratory responses to physiological stress and provide insight regarding the integrity of the pulmonary-vascular interface and characterization of any impairment or abnormal cardio-respiratory function.

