### 3.5 Ethical Considerations

#### 3.5.1 Consent

Eligible patients will be identified at the designated PIC sites (STH, Sheffield; UIC, USA and Ramaiah, India) by individuals knowledgeable about the research. The researcher will introduce themselves to the patient and/or patient representatives and explain the nature of their visit to the patient. The researcher will proceed, if the patient agrees, to discuss the nature, objective, risks, and benefits of the proposed research. This will include the provision of written information regarding the research study, implications, expected outcomes, risks, and benefits. The patient will be allowed to ask questions throughout this process.

Once patients have indicated their willingness to participate in the research, they will be invited to a session at their local site. Consent will be obtained by members of the research team and documented using the study consent form. Informed consent will be obtained before the participant undergoing any activities that are specifically for the study. All study documentation (i.e. participant information sheet, participant consent form) will be kept in the Trial Master File.

The right of the patient to refuse to participate in the study without giving any reason must be respected. Equally, the patient will be free to withdraw their consent to participate in the study without providing any reasons and without prejudicing his or her further treatment.

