## **4.0 Study Protocol**

Each test will be interpreted following published guidelines provided by the American College of Sports Medicine. Upon the conclusion of each test, the key descriptive characteristics and findings will be recorded to facilitate the use of cohort analyses. Data will be stratified according to the demographic (age, gender, ethnicity, pre-COVID-19 functional status and important physiological parameters for a given workload (absolute and relative oxygen consumption or  $VO_2$  peak,  $O_2$  pulse, alveolar-arterial  $O_2$  gradient, arterial to end-tidal  $CO_2$  difference and the relationship between carbon dioxide output and ventilation ( $V_E/VCO_2$  slope))). These approaches will be used to identify differences, trends and patterns in key defining variables that might lead to longstanding impairment/morbidity. Study day 1 will be conducted 7-10 days post baseline measures to ensure no symptoms of post exertional malaise and/or excessive fatigue from baseline assessments. Patients will wear accelerometers during this period to compare baseline and follow up.

Baseline	Session 2	Session 3 (+1 day)	7 Day follow up
Anthropometrics Questionnaires Symptom Profile* Lung Function TUG 6MWT	Symptom Profile* ECG Resting HR + BP CPET Lactate and BP Recovery following CPET HRV	Symptom Profile* ECG Resting HR + BP CPET Lactate and BP Recovery following CPET HRV	Accelerometry Patient Log/Diary HRV

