#### *4.1.6 Cardiopulmonary Exercise Test (CPET) (Session 2 and 3)*

Cardiopulmonary exercise testing will be performed to measure VO2 peak and other parameters representative of cardiovascular reserve (McGregor et al., 2016). Tests will be conducted using a standard bicycle ramp protocol in accordance with American Thoracic Society guideline (Ross et al., 2003). In accordance with pilot data, we will stratify individuals starting load based on their 6MWT distance, Strata I: 6MWD < 350 (starting load of 10 watts; with subsequent increments of 5 watts), Strata II: 6MWD 350 – 400 (starting load of 20w with subsequent increments of 5w and Strata III: 6MWD > 400 (starting load of 30w with subsequent increments of 5W)

Participants will then complete a maximal graded exercise test on a friction-loaded cycle ergometer (Monark 894E Ergomedic Peak Bike, Monark, Varberg, Sweden). The cycle ergometer friction wheel will be calibrated according to manufacturer recommendations prior to the study. The cycle ergometer will be set up according to each participant's body size and personal preference. The knee angle at the bottom of the pedal stroke will be ~25°, which is optimal for movement economy and injury prevention. Knee angle will be measured using a universal goniometer. The cycle ergometer handlebars will be positioned so that the participant can comfortably maintain an upright posture. The cycle ergometer set-up will be identical for each visit.

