## 10.0 Discontinuation/Withdrawal of Participants from Study Treatment

Each participant has the right to withdraw from the study at any time. Participants may be withdrawn from the study either at their request or at the discretion of the Chief Investigator. Participants will be made aware (via The Participant Information Sheet and Participant Consent Form) that withdrawing the data which has been collected cannot be erased and may still be used in the final data analysis and study dissemination (i.e. published journal). The Chief Investigator may withdraw a participant from the study at any time if they consider that the participant's health is compromised by remaining in the study or the participant is not sufficiently cooperative. The reasons for any participant withdrawal will be recorded on the study completion form of the CRF. The data collected from withdrawn participants will be included in the study report.

Besides, the Chief Investigator may discontinue a participant from the study at any time if they consider it necessary for any reason including but not limited to:

- Ineligibility (arising during study or retrospective having been overlooked at screening)
- Significant protocol deviation
- Significant non-compliance with study requirements
- An AE which results in the inability to continue to comply with study procedures
- Progression of illness that renders participants unable to comply with study procedures.
- Consent is withdrawn
- Lost to follow up

The reason for withdrawal will be clearly stated and recorded in the CRF.

If the participant is withdrawn due to an AE, the Chief Investigator will arrange for a follow-up telephone call until the AE has resolved or stabilised.

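### Removing participants whose 6-minute walk test provokes post-exertional malaise conflicts with the secondary aim of estimating how common that malaise is

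*Protocol*

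**What the plan says.** One of the four secondary aims in Protocol Section 2.2 is: "Examine the prevalence of post-exertional malaise in people with long covid".

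Section 4.1.3, on the 6-minute walk test (6MWT), states: "Patients suffering from excessive fatigue/Post exertional malaise from the 6MWT will be excluded from the study to prevent further onset of these symptoms". Neither the eligibility list in the synopsis nor the one in Section 3.3 contains this rule.

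The 6MWT is a study procedure. The Baseline column of the Section 4.0 schedule reads "Anthropometrics Questionnaires Symptom Profile* Lung Function TUG 6MWT", and the first cardiopulmonary exercise test (CPET) follows 7-10 days later. Section 3.5.1 states: "Informed consent will be obtained before the participant undergoing any activities that are specifically for the study".

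On timing, Section 4.1.3 says of the 6MWT and the timed up and go test: "Two different assessments of lower extremity functional capacity will be conducted at each visit". The Section 4.0 schedule lists the 6MWT at baseline only. Section 4.1.6 relies on a walk distance being available before CPET: "we will stratify individuals starting load based on their 6MWT distance".

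Three other sections bear on those removed.
- Section 10.0 says "The data collected from withdrawn participants will be included in the study report" and "The reasons for any participant withdrawal will be recorded on the study completion form of the CRF".
- Section 4.4.3 provides for screening for PEM before the study, follow-up after baseline, and pacing guidance for those with symptoms. It states no exclusion.
- Section 4.2 collects accelerometry, heart rate variability and a daily wellness score for 3 days after baseline and after CPET.

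**The concern.** PEM is both the condition to be counted and a named ground for leaving the study. Those removed have already consented and undergone a study assessment, so this is not ordinary screening that defines the target population in advance. The aim still refers to people with long COVID, not to people with long COVID who tolerate a 6MWT.

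If those removed drop out of both numerator and denominator, the reported percentage describes the second group. Recruiting more participants would narrow the confidence interval but would not remove the bias.

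The rule also merges PEM with excessive fatigue, and Section 4.2 collects a wellness score without a PEM criterion. If the two grounds are not separated when a participant is removed, no later analysis can separate them.

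**Working it through.** **Text against text.** The protocol states no PEM rate, so there is no figure to reproduce. Set side by side:
- Section 2.2 fixes the target as people with long COVID.
- Section 4.1.3 removes from the study those with PEM or excessive fatigue from the 6MWT.
- Sections 3.5.1 and 4.0 show that removal comes after consent and, for the baseline test, before both CPETs.
- Section 10.0 keeps the data of withdrawn participants in the report. It does not say whether these people count as cases or stay in the denominator.

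**Model for literal exclusion.** Let p be the true PEM prevalence among those enrolled, s the share of PEM cases removed, and f the share of non-cases removed (for fatigue). All three are assumed. N = 150 before removal is the planned total (50 per centre).

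Observed prevalence = p(1−s) / [p(1−s) + (1−p)(1−f)]

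Remaining n = 150 × [p(1−s) + (1−p)(1−f)]

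The bias is downward if s > f, zero if s = f, and upward if s < f.

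**Worked values at p = 0.5, s = 0.3.**
- f = 0: 0.35/0.85 = 41.2%, n = 127.5
- f = 0.1: 0.35/0.80 = 43.75%, n = 120
- f = 0.2: 0.35/0.75 = 46.7%, n = 112.5
- f = 0.3: 0.35/0.70 = 50.0%, n = 105

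Upward case, p = 0.5, s = 0.1, f = 0.2: 0.45/0.85 = 52.9%.

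**Other prevalences, s = 0.3.**

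| p | f = 0 | f = 0.1 | f = 0.2 |
|---|---|---|---|
| 0.3 | 23% | 25% | 27% |
| 0.7 | 62% | 64% | 67% |

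**Against sampling error.** The bias exceeds the 95% half-width, 1.96 × √[observed(1−observed)/n] at the reduced n, only when s is above about:

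| p | f = 0 | f = 0.1 | f = 0.2 |
|---|---|---|---|
| 0.3 | 0.31 | 0.39 | 0.47 |
| 0.5 | 0.29 | 0.375 | 0.46 |
| 0.7 | 0.33 | 0.41 | 0.49 |

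At p = 0.5 the remaining n at these thresholds is about 128, 114 and 101, and the half-widths are 0.085, 0.090 and 0.096.

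**Check of the proposed repair.** Split s into s1 (removed for PEM) and s2 (removed for fatigue alone, but would have had PEM after CPET). Keep everyone in the denominator and count s1 as cases. Counting fatigue-only removals as non-cases gives p(1−s2). Counting them as cases gives p + (1−p)f. This interval always contains p.

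Example with p = 0.5, s1 = 0.2, s2 = 0.1, f = 0.1:
- 75 of 150 have PEM: 15 are removed for PEM, 7.5 for fatigue alone, and 52.5 remain.
- Of the 75 without PEM, 7.5 are removed for fatigue.
- Literal exclusion: 52.5/120 = 43.75%.
- Repair, lower bound: (52.5 + 15)/150 = 45%.
- Repair, upper bound: (52.5 + 15 + 15)/150 = 55%.

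**The case against.** The strongest reply is that the protocol, read as a whole, already observes and keeps these people. Section 10.0 retains their data and records why they left, Section 4.2 covers the days after the baseline walk, and Section 4.4.3 follows them up. The stated purpose of the rule is protective, so it may mean only that exertion stops. On that reading, the denominator and case definition belong in a statistical analysis plan. Prevalence might also be taken from the pre-study screen, the sample was never representative of all long COVID, and every rate in the illustration is assumed.

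Part of this stands. The bias is conditional on the literal reading, its size is unknown, and it may be smaller than sampling error. The disagreement over visits does not itself establish bias.

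The rest does not dispose of the point. The wording is exclusion from the study, and including data in a report does not place a person in a numerator or denominator. A prevalence taken from the pre-study screen would be altered in the same way if those removed were dropped from it. Other limits on representativeness do not justify selecting on the outcome itself. An analysis plan can define a denominator, but it cannot recover a PEM-versus-fatigue distinction that was not recorded at the visit.

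**Conclusion.** The concern holds. As written, the exclusion in Section 4.1.3 conflicts with the PEM aim in Section 2.2 and, followed literally, selects the sample on the outcome.

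Only the condition for its direction is supported: prevalence is understated if PEM cases are removed more often than non-cases. That is likely, because PEM is a named ground for removal, but not assured. The documents support no numerical size.

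The effect falls on one of four secondary aims and leaves the primary aim untouched. It should be fixed, with moderate confidence in its practical importance. The contradiction about which visits include the 6MWT is plain from the text and needs reconciling whatever the size of the bias, since on the wording of Section 4.1.3 removal could also follow a walk at Session 2 or 3.

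**What to change.** Leave the rule on who proceeds to CPET unchanged, and amend the counting and recording:

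1. State that participants removed after the 6MWT stay in the PEM prevalence denominator, defined as all consented participants who performed the baseline 6MWT.
2. Count as a case anyone with PEM after the 6MWT or after CPET. Report the two components separately, and label the CPET component as conditional on tolerating the 6MWT.
3. State that those removed for fatigue alone were not observed after CPET, and report prevalence with them counted first as non-cases and then as cases.
4. Record on the CRF whether removal was for PEM or for fatigue alone, and the criterion used. Keep their baseline and 3-day post-baseline data, subject to consent.
5. Reconcile Section 4.1.3 with the Section 4.0 schedule on which visits include the 6MWT, so that it is clear when the exclusion can apply.

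The cost is small: one population and case definition, one schedule clarification and one added CRF item, made through the protocol's amendment process. The walk test, the 3-day follow-up and a recorded withdrawal reason are already planned. The PEM criterion and the PEM-versus-fatigue split are new and must be written.

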#### **4.1.4 Lung Function (Session 1)**

Full lung function tests including FEV1, FVC, PEFR, flow-volume curves, MIP, and MEP will be conducted during first visit. These spirometry measurements will be conducted by a suitably qualified individual, proficient in the use of the specific equipment and according to published standards.

#### *4.1.5 ECG and Blood Pressure (Session 2 and 3)*

Participants will then be fitted with: a 12-channel electrocardiography (ECG) device (Custo Cardio 200, Customed, Ottobrunn, Germany); a blood pressure cuff positioned over the brachial artery (Tango M2, SunTech, Eynsham, UK). Measurements will be taken following 10 minutes of supine rest, during sit to stand task and monitored continuously throughout the CPET.

#### *4.1.6 Cardiopulmonary Exercise Test (CPET) (Session 2 and 3)*

Cardiopulmonary exercise testing will be performed to measure VO2 peak and other parameters representative of cardiovascular reserve (McGregor et al., 2016). Tests will be conducted using a standard bicycle ramp protocol in accordance with American Thoracic Society guideline (Ross et al., 2003). In accordance with pilot data, we will stratify individuals starting load based on their 6MWT distance, Strata I: 6MWD < 350 (starting load of 10 watts; with subsequent increments of 5 watts), Strata II: 6MWD 350 – 400 (starting load of 20w with subsequent increments of 5w and Strata III: 6MWD > 400 (starting load of 30w with subsequent increments of 5W)

Participants will then complete a maximal graded exercise test on a friction-loaded cycle ergometer (Monark 894E Ergomedic Peak Bike, Monark, Varberg, Sweden). The cycle ergometer friction wheel will be calibrated according to manufacturer recommendations prior to the study. The cycle ergometer will be set up according to each participant's body size and personal preference. The knee angle at the bottom of the pedal stroke will be ~25°, which is optimal for movement economy and injury prevention. Knee angle will be measured using a universal goniometer. The cycle ergometer handlebars will be positioned so that the participant can comfortably maintain an upright posture. The cycle ergometer set-up will be identical for each visit.

A step-wise incremental exercise test will be performed at a cadence of 60 revolutions per minute (rpm) ( $\pm 10\%$ ). The exercise protocol will begin with a 3-minute rest period, followed by a step-wise incremental protocol, designed to achieve volitional exhaustion within 8-12 minutes of exercise onset. The exercise protocol will be individualised based on participants' predicted exercise capacity, as described above. Heart rate and pulmonary gas exchange data will be measured continuously. Blood pressure and rating of perceived exertion (RPE) (6 to 20 scale) will be measured during the final 15 second period of each minute. For blood pressure measurements, participants will be asked to relax their arm and shoulder muscles whilst their forearm is rested on the researcher's shoulder (padded with a folded towel). This will ensure that the participant's arm is positioned near heart level to reduce measurement error. At the end of the exercise test, participants will complete a cooldown consisting of unloaded pedalling at 20rpm for 5-10 minutes. All data will be exported for offline analysis using Microsoft Excel (Washington, USA).

Criteria for the assessment of a good participant effort will include peak respiratory exchange ratio (RER)  $>1.10$ , peak HR $\geq 85\%$  predicted and RPE  $\geq 18.31$  (Balady et al., 2010). Prior to the test, participants will be monitored for 5 minutes to allow passive data collection and for a total of 10 minutes after completion.

We will analyse over 30s averages to allow for differences in Gas analysis systems and monitor heart rate throughout test and 10 minutes seated recovery. Blood Pressure monitoring continuously (every 30s). Blood lactate concentration will be monitored through fingertip sampling at the end of each stage and at 5-minute intervals for 30 minutes following volitional fatigue.

